### **Research Design and Methodology:**

The proposed research will use a novel approach to distinguish the short-term effects on LBP of physical activities from the long-term effects of such activities, by conducting a longitudinal case-crossover study nested within a cohort study. This design accounts for measured and unmeasured confounds by using each case as his/her own control- an entirely observational study that is analogous to a crossover experiment- capitalizing on modern mobile health and actigraphy technology. The primary exposures of interest are 10 self-reported physical activities commonly performed during work and activities of daily living, and actigraphy-assessed physical activity. The primary outcomes are participant-reported “flares” of low back pain (Aim 1) and participant-reported back-related functional limitations (mobility and activities of daily living [ADLs]) at 1-year follow-up, as measured by the Roland-Morris Disability Questionnaire. This observational study will include up to 730 Veterans with LBP aged 18 and older recruited from the VA Puget Sound Health Care System (VAPSHCS). The study will not affect Veterans’ medical care in any way. After verbal informed consent, recruitment, and baseline data collection, study participants will complete frequent, serial electronic “e-Questionnaires” using their own personal electronic devices (personal computer [PC], tablet, or smartphone) over the 1-year period of follow-up. Participants may also wear ActiGraph units for the 1st 4 weeks of follow-up. Long-term outcomes will be assessed by extended e-Questionnaires completed at 1-year follow-up. Aim 1 analyses will examine the short-term effects of 10 specific activity categories on participant-reported flares across all study assessments over 1-year follow-up. Aim 2 analyses will examine associations between the frequency of exposure to 10 specific activity categories over weeks 1-4 of follow-up, and long-term functional recovery at 12 months as defined by the RMDQ. All analyses will use a biopsychosocial framework accounting for potential confounders (sociodemographics, psychological factors, etc.) and effect modifiers, and will include sensitivity analyses to examine the robustness of findings and important study assumptions.

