
Please see “Overview of the Overall Study Approach” subsection in 3.0 above. As mentioned, the study as a whole involves two separate components: (1) a VA component involving all VA recruitment, VA data collection, and all processes involving VA data (addressed by the current VA IRB application and referred

to as the “VA component”), and (2) a non-VA component involving non-VA data collection that occurs entirely outside the VA and does not involve any VA data. Non-VA data collection involves e-Questionnaires (referred to as “e-Surveys” in participant-facing materials). e-Questionnaires are to be administered as part of the non-VA (UW) research processes and are therefore provided to the VA IRB for completeness, but not for VA review. E-questionnaires are labelled as Attachments Q1-Q3.

ActiGraph units will not be available for participant use by the time when recruitment could otherwise be started. ActiGraph-related research questions are separate from the primary study aims which rely on participant-reported data, and are therefore non-essential and optional for participant use. Participants may or may not be offered to wear an ActiGraph and use of this device is optional. Due to the expected unavailability of ActiGraph units at the time when recruitment is started, potential participants approached at times when Actigraphs are not available will be offered the opportunity to participate without wearing the ActiGraph. With the current version of the protocol, we provide a revised Information Statement document that describes participation in the study either with or without participation in that component of the study that involves the ActiGraph. In other words, the revised Information Statement is now applicable whether or not the participant wears the ActiGraph as part of their study participation.

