25% based on a previously conducted pilot study), (3) number of case/control periods, and (4) proportion of participants who are statistically informative (with both case and control periods). Given the transient nature of flares, in our view, only activity exposures with moderate magnitude effects (ORs of 1.5-2.0) will have a meaningful impact on the population level. Informed by the characteristics of activities, flares, and missing data from our pilot, we estimated power using simulated data with 1000 replications, assuming  $\alpha=0.005$  (Bonferroni-corrected for 10 activity groups), comparing different assumptions for sample size determinants, including activity frequencies as low as 3%. A sample size of  $n=440$  yielded  $\approx 90\%$  power to detect ORs of 1.5 for activity frequencies  $\approx 10\%$ , 80% power to detect OR=1.6 at activity frequency=5%, and 80% power for OR= 1.81 given activity frequencies as low as 3% (**Figure 2**). Allowing for 40% of participants not being analyzed due to having limited data available (loss to follow-up, fail run-in period, etc.), this yielded **a planned sample size of  $n=730$  for Aim 1**. These power estimates are highly conservative, since (1) they use data from scheduled e-Questionnaires only and assume no data from *ad hoc* flare-window e-Questionnaires, and (2) they assume no information at all from the  $n=290$  with limited data. Moreover, they are based on binary activity exposures, and analyses using continuous exposures (incorporating duration and frequency) will have greater power. As a point of comparison, the previously conducted pilot study was able to detect ORs  $\geq 2.5$  and  $p$ -values  $< 0.001$  despite having  $\sim 9x$  fewer participants than the currently proposed study. For Aim 2, using the same data simulated for Aim 1, and assuming an expected mean (standard deviation) 1-year RMDQ scores of 8.8 (6.4) from a prior study, Bonferroni-corrected  $\alpha=0.005$ , activity frequencies  $\approx 20\%$ , and  $n=440$  without missing data (from  $n=730$  initially recruited), we estimated power over a range of scenarios where we varied the strength of the association between the *change* in activity frequency over the 1st 4 weeks of follow-up (for each of the 10 activity categories) and a minimum clinically important change in 1-year RMDQ of 2.5 points. We found  $\geq 80\%$  power to detect a 2.5-RMDQ-point difference at 12 months in scenarios where a 65% change in activity frequency over the 1st 4 weeks produced a 2.5-RMDQ-point difference at 12 months, and in all scenarios where the activity frequency-RMDQ relationships was *more* extreme (e.g., if a smaller % change in activity frequency produced a 2.5-RMDQ-point difference at 12 months. This confirms adequate power with **a planned sample size of  $n=730$  for Aim 2**.

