**5.6.2 a. Aim 1 analyses:** We will examine associations between activity group exposures and the participant-reported flares outcome in conditional logistic regression models, using data from all scheduled and flare window e-Questionnaires over 1- year. There will be one model for each of the 10 primary activity categories. Models will include activity categories as time-varying predictors as in **equation 1**, where  $Y$  is the outcome (flare vs. no flare),  $x$  is the activity

exposure (yes vs. no), and  $C$  represents potential time-varying confounders (psychological factors, other activities). The letter  $i$  indicates the  $i^{\text{th}}$  individual ( $i = 1, 2, \dots, n$ ),  $j$  indicates the  $j^{\text{th}}$  time of follow-up ( $j = 1, 2, \dots, n_i$ ) and  $x_{i(j-1)}$  indicates an activity that was performed in the exposure window prior to the  $j^{\text{th}}$  time (either the start of the control window [scheduled e-Questionnaire] or time of flare onset [flare window e-Questionnaire]). As previously noted, the survey methods are such that activity exposure and flare outcome are inherently time-lagged, with exposure preceding outcome.  $\beta_w$  represents the association of activity  $x$  with flare outcome  $Y$  within individuals (the ‘within-individual effect’), or the expected odds of a flare with change in the activity exposure for a given individual. These analyses will yield odds ratios (OR) and 95% confidence intervals for within-individual ‘effects’ of activity triggers on an LBP flare. The initial analytic approach (**Figure 3**) will examine the association between binary activity exposure and binary flare outcome, with explicit adjustment for pain NRS and number of prior flares measured at time= $j-1$ , and time-variant confounders selected based on conceptual importance; *by design*, the case-crossover method uses each person as their own control, accounting for known and unknown confounds that are fixed or relatively stable over time (i.e., age, sex, sociodemographics, medical and LBP history, work-related factors, and underlying psychological predispositions). We will use a Bonferroni-corrected threshold of  $p=0.005$  for each

$$\log \left[ \frac{Pr(Y_{ij} = 1)}{1 - Pr(Y_{ij} = 1)} \right] = \beta_{0i} + \beta_w x_{i(j-1)} + \gamma C_{i(j-1)}, i = 1, 2, \dots, n; j = 1, 2, \dots, n_i \quad (1)$$

[figure not shown]

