\*Analysis includes all scheduled and flare window e-Surveys. Activity exposures over prior 24-hr and 2-hr effect periods, and current flare status, are inherently time-lagged.

primary activity-

flare comparison to account for 10 statistical comparisons (one for each of the 10 activity categories). We will further examine for activity-flare associations after accounting for important relationships based on theory and clinical knowledge, including the following: dose-response relationships; work- specific activity-flare associations; multivariate analyses including other potential confounders (other time-varying activities, depression, PTSD, stress, catastrophizing); potential moderators; different effect-periods of activity exposures (i.e., 24 vs. 2 hours); possible biases (e.g., conscious activity avoidance and carry-over effects); and clinical subgroup analyses (lumbosacral radicular syndrome [LSRS] symptomatic lumbar spinal stenosis [SLSS] diagnosed by a specialist, ascertained by chart review). We will also conduct similar subgroup analyses as secondary analyses, targeting the expanded target population subgroups described above (facet-mediated pain, SIJ-mediated pain, spondylolysis, ascertained by EHR review). We will analyze the reliability and accuracy of these subgroups. Of note, the primary analysis of walking, standing, and sitting will use the ActiGraph data (which are only obtained for the 1st 4 weeks of follow-up); secondary analyses will use the self- reported data for these 3 groups over the entire 1-year follow-up, and will also examine the association between ActiGraph and self-reported data. After these analyses using the binary flare outcome, we will use an analogous approach to examine relationships between activity categories and the secondary (continuous) outcome of NRS LBP intensity, with linear mixed-effects regression. These analyses account for potential biases that might be introduced by participant self-identification of flare status; if no such bias exists, we would expect the direction of effects to be similar to those obtained in the initial analysis of flares.

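### Sections 5.6.2a and 5.1 disagree on whether optional four-week ActiGraph data or self-report is primary for walking, standing and sitting, and the Aim 1 power text describes no ActiGraph-based test

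*Combined protocol and SAP*

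**What the plan says.** - **Section 5.6.2a (Aim 1 analyses).** The ten models are fitted "using data from all scheduled and flare window e-Questionnaires" over one year, each tested at p=0.005, and the initial model "will examine the association between binary activity exposure and binary flare outcome". The same section then says that "the primary analysis of walking, standing, and sitting will use the ActiGraph data". It notes that these data exist only for the first four weeks and makes full-year self-report a secondary analysis for the three activities.
- **Section 5.1 (Study Design).** The ActiGraph questions are "separate from the primary study aims which rely on participant-reported data, and are therefore non-essential and optional for participant use". It also says that "ActiGraph units will not be available for participant use by the time when recruitment could otherwise be started" and that participants may or may not be offered a device.
- **Abstract (Research Design and Methodology).** The primary exposures are "10 self-reported physical activities commonly performed during work and activities of daily living, and actigraphy-assessed physical activity", so both sources are listed.
- **Section 5.6.1 (Sample Size Calculations).** For n=440 and alpha 0.005 it gives about 90% power for an odds ratio (OR) of 1.5 at activity frequency of about 10%, 80% for OR 1.6 at 5%, and 80% for OR 1.81 at 3%. Expected frequencies are 5-25%. Of these estimates it says that "they use data from scheduled e-Questionnaires only", and it adds that exposure is binary. It also holds that "only activity exposures with moderate magnitude effects (ORs of 1.5-2.0) will have a meaningful impact on the population level".
- **Section 5.5 (ActiGraph data collection).** Existing algorithms will classify activity type. People who do not want the device may take part without it.

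**The concern.** Walking, standing and sitting are three of the ten comparisons over which the 0.05 error rate is split. Which result is primary for them depends on which section is followed. The two data sets differ in length (four weeks or one year), in who contributes (optional wearers or all participants) and in how exposure is measured. Section 5.6.3 uses walking as its worked example of weighing short-term against long-term effects, so the designation bears on the study's intended output.

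The power statement is attached to Aim 1 as a whole and is called highly conservative. Its stated reasons are that flare-window reports and participants with limited data are ignored. Neither reason addresses a shorter window or a wearer subset.

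**Working it through.** **1. The sections compared.** Within 5.6.2a, the sentence on the three activities can be read as a stated exception to the general model, so those two statements are compatible. Section 5.1 cannot be read that way, because it takes ActiGraph out of the primary aims altogether. The Abstract names both sources and does not break the tie.

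**2. The plan's own figures.** Alpha: 0.05/10 = 0.005, as stated. Sample size: 440/(1 - 0.40) = 733.3, rounded up to 734, against 730 stated; 730 - 290 = 440. The power simulation cannot be rerun, because the text does not give the flare frequency, the number of periods per person or the share of informative participants, and Figure 2 is not shown. I therefore calibrated an approximation for within-person conditional logistic regression to the stated results:

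power = Φ( ln(OR) × √(N × K × p(1-p)) - 2.807 )

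N is the number of people and p the activity frequency. K is the information per person: the mean of m(T-m)/T, with m flare assessments out of T. The value 2.807 is the normal quantile for two-sided alpha 0.005 (two-sided is assumed). Solving for K:

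- OR 1.5, p = 10%, 90% power: ((2.807+1.282)/0.4055)² = 101.7; 101.7/(440×0.09) = 2.57
- OR 1.6, p = 5%, 80% power: ((2.807+0.842)/0.4700)² = 60.3; 60.3/(440×0.0475) = 2.88
- OR 1.81, p = 3%, 80% power: ((2.807+0.842)/0.5933)² = 37.8; 37.8/(440×0.0291) = 2.95

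The three scenarios are broadly consistent with each other. K = 2.57-2.95 is used below.

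**3. Share of data in the ActiGraph period.** Scheduled assessments number 3×4 + 1×4 + 2×10 = 36, which matches the payment cap in 5.2.7. Twelve fall in weeks 1-4, so K becomes K/3 = 0.857-0.983.

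**4. Illustrative power for OR 1.5 from weeks 1-4.** No uptake is stated; full and half uptake are assumptions. Example at 10%, all wearing, K = 2.57: √(440×0.857×0.09) = 5.82; 0.4055×5.82 - 2.807 = -0.45; Φ = 33%.

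| Activity frequency | All 440 wear it | Half (220) wear it |
|---|---|---|
| 10% | 33-39% | 13-15% |
| 25% | 73-80% | 35-41% |
| 50% | 87-92% | 49-57% |

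The OR detectable with 80% power, exp(3.649/√(N×(K/3)×p(1-p))), is 1.79-1.87 (all) or 2.29-2.43 (half) at 10% frequency, and 1.50-1.54 or 1.77-1.85 at 25%. A conditional logistic simulation with the flare rate tuned near 6% gave 34-35% and 14-17% for the 10% row. Because the rate was tuned, this checks the formula and does not reproduce the plan's figure.

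**5. Full-year self-report when exposure is very common.** With 440 people, 36 assessments and OR 1.5:

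- 95% frequency, p(1-p) = 0.0475: power 57-65%
- 98% frequency, p(1-p) = 0.0196: power 18-22%

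The frequency of these three activities over 24 hours is not stated.

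**The case against.** Section 5.6.2 calls all analyses preliminary. Section 5.6.2a discloses the four-week limit, keeps full-year self-report and plans to compare the two sources. So no data are lost, and the other seven activities are unaffected. This stands and limits the seriousness. It does not reconcile two current statements about what is primary.

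A reader might infer that no ActiGraph power was ever calculated. The documents do not support that: Figure 2 is not shown, and only the absence of a described calculation can be asserted. Section 5.6.1 also states its questionnaire-based, binary footing openly, so extending its power to all ten tests is the reader's inference.

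A reader might also infer that the ActiGraph exposure is undefined. Section 5.5 names existing algorithms that distinguish sitting and standing, and cites validation for walking. The gap is narrower: no yes/no cut-point is given for the binary model, and 5.6.2 leaves categorisation to clinical rationale or distribution.

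Finally, the illustration may be pessimistic. The 440 are one-year completers, and later dropouts among up to 730 recruits can supply weeks 1-4 data. With 550-600 contributors (an assumption), the formula gives 84-93% at 25% frequency, against 73-80% with 440. Flare-window reports and continuous exposure would also help. Non-wear, or near-universal exposure, would pull the other way.

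**Conclusion.** The point holds and should be fixed. Sections 5.6.2a and 5.1 contradict each other on the primary exposure source for three of the ten Aim 1 tests. The text of 5.6.1 describes no device-based, four-week or wearer-only scenario, so the stated 80-90% cannot be taken to cover those tests. Confidence in these two statements is high.

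The figures are illustrations. They rest on assumed uptake, two-sided alpha, equal completion across the 36 scheduled assessments, binary exposure and information calibrated to the plan's own results. It would be tempting to conclude that the three tests are underpowered. The documents do not support that: for OR 1.5, the illustration runs from 13% to 92% depending on uptake and exposure frequency, neither of which is stated for these activities. Nor can a reader assume that switching to full-year self-report secures the stated power, because that depends on frequencies lying within the range simulated.

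**What to change.** Reconcile 5.6.2a with 5.1, and clarify the Abstract and the general model statement in 5.6.2a, so that one source is primary for walking, standing and sitting. State in 5.6.1 which tests the quoted power covers. Two routes are open, and the choice is the sponsor's.

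- **(a) Full-year self-report primary**, with ActiGraph as secondary and validation analyses. Add that the 5.6.1 power applies only if the 24-hour frequency of these activities lies in the range simulated. Downside: less accurate measurement and possible differential recall, since flare-window items ask about earlier activity after flare onset.
- **(b) ActiGraph primary.** Revise 5.1, state that the 5.6.1 power does not apply to these three tests, and give a weeks 1-4, wearer-only power or detectable OR with assumed uptake. Prespecify a cut-point or a continuous measure. Downside: fewer assessments and self-selected wearers.

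The cost is protocol wording, plus one power calculation under (b). Neither route needs new data collection.

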Payments will be bundled together to minimize inconvenience to participants and for reasons of feasibility, into 3 payment periods after the end of month 2, month 7, and months 12 (completion of study). If a participant withdraws from the study at another time that is not close in time to these 3 payment periods, a payment will be initiated at the time of withdrawal. The time points for payments and spacing between payments are motivated by our experience with current and recent VAPSHCS studies, including that it sometimes takes approximately 5 months after a payment is sent before we can confirm with the participant that the payment has been received. Tracking of non-VA (e-Questionnaire) data collection completion by VA staff for the purposes of participant payments is feasible because a researcher-facing portal for participant tracking will be accessible to VA research staff as part of the non-VA study processes. This portal can be accessed when needed to determine the applicable payment amounts at the time of each payment period.

5.2.8 Periodic contacts by phone, when needed Participants may be contacted by study staff via telephone in certain instances where data indicates participant misunderstanding about aspects of data collection or the study in general, or to respond to participant-initiated questions left on the study voicemail. During these conversations, research staff will be guided by the content provided in the Reminder Call Script (Attachment R). Participants may be contacted if they attempt to complete a Flare-window e-Questionnaire while also reporting that they are not having a flare (indicating misunderstanding about the flare definitions being used, or the expectations for reporting); for repeated missed Scheduled e-Questionnaires; for not completing any

flare-window e-Questionnaires; for reporting non-wear of the ActiGraph during 2 or more assessments during the 1st 4 weeks; for problems related to the ActiGraph or returning the ActiGraph, or other questions prompting an a direct telephone contact; or similar occurrences reflecting a misunderstanding of or lack of compliance with study processes. Some telephone contacts with participants are advantageous to allow participant-staff interactions and maintain connectedness with the study, beyond what can be achieved electronically. These contacts thus ensure validity of the study findings.

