**All other study evaluations as described immediately below will be conducted as part of the e-Questionnaires that are non-VA data collection. These are presented here for the sake of completeness, although their initial conduct/acquisition are not a part of the VA component of the research.** After acquisition as part of the non-VA component of this research, the data will be shared with the VA study team, and henceforth will become VA data. The baseline e-Questionnaire will be administered within 2 days of a participant completing informed consent. Scheduled e-questionnaires will be administered 3 times weekly during weeks 1-4, once a week during weeks 5-8, and twice a month from months 2-12. The exit e-Questionnaire will be administered at 1-year follow-up. Flare window e-Questionnaires are completed on an ad hoc basis during the 1-year follow-up period, and are participant-initiated (not on a set schedule)

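### The NRS pain model offered as the check on flare self-identification bias names no record set; if it pools flare-window records, it cannot detect selective logging of flares

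*Combined protocol and SAP*

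**What the plan says.** The primary Aim 1 flare model in section 5.6.2a is a conditional logistic regression "using data from all scheduled and flare window e-Questionnaires over 1- year". The footnote to Figure 3, which shows that flare analysis, repeats this: "Analysis includes all scheduled and flare window e-Surveys".

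For pain intensity, the same section says that "we will use an analogous approach to examine relationships between activity categories and the secondary (continuous) outcome of NRS LBP intensity, with linear mixed-effects regression". No record set is given for this model.

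Two statements about its purpose follow. The first is "These analyses account for potential biases that might be introduced by participant self-identification of flare status". The second is "if no such bias exists, we would expect the direction of effects to be similar to those obtained in the initial analysis of flares".

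Section 5.5 describes flare-window e-Questionnaires as started by the participant, with no fixed schedule and with the same content as the scheduled ones, so they include NRS. Section 5.2.8 shows that they are meant to be completed only during a flare: "Participants may be contacted if they attempt to complete a Flare-window e-Questionnaire while also reporting that they are not having a flare". Scheduled e-Questionnaires are cued by an alert and also ask for flare status (section 5.1). Section 5.2.7 shows that the sponsor has considered over-reporting of flares: payment falls after the 10th flare e-Questionnaire and stops after the 30th.

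**The concern.** Self-identification of a flare acts at two points. It decides how a participant labels a given pain level. It also decides whether a flare-window record exists at all. Changing the outcome from flare status to NRS deals with the first and leaves the second in place.

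Suppose a participant who has just lifted something heavy, and blames lifting, is more likely to log the pain that follows than the same pain on another day. The extra records then contain more lifting and, if pain is higher during logged flares, higher NRS. The flare OR and the NRS slope for lifting both rise although lifting has no effect.

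Agreement in direction is what the plan expects when there is no bias. It is also what selective logging produces, so the comparison cannot separate the two. A false trigger could then appear supported by a second outcome and pass into the tables of risk estimates that section 5.6.3 links to activity recommendations.

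**Working it through.** The plan gives no figure for this check, so there is none to reproduce. The question is how far selective logging alone moves the NRS slope when activity has no effect on pain.

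**Inputs from the documents**
- Scheduled records per person: up to S = 36 (section 5.2.7).
- Participants analysed: 440; threshold 0.005 per activity (section 5.6.1).
- Activity frequency: 10%, within the expected 5–25% (section 5.6.1).

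**Assumptions, not in the documents**
- F = 10 flares per person-year that could be logged.
- NRS in flare-window records d = 2.5 points above scheduled records.
- Within-person SD of NRS 1.5.
- Logging probability q1 if exposed, q0 = 0.30 if not.

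**Expected slope, all records.** Among exposed records the flare-window share is s1 = F·q1/(S + F·q1). Among unexposed records it is s0 = F·q0/(S + F·q0). Activity frequency cancels. The spurious within-person slope is d·(s1 − s0), with s0 = 3/39 = 0.0769.

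| q1 vs q0 | s1 | d·(s1 − s0) | Simulated slope | Simulated p<0.005 |
|---|---|---|---|---|
| 0.60 vs 0.30 | 6/42 = 0.1429 | 0.165 | +0.16 | 87% |
| 0.45 vs 0.30 | 4.5/40.5 = 0.1111 | 0.085 | +0.09 | 22% |
| 0.36 vs 0.30 | 3.6/39.6 = 0.0909 | 0.035 | +0.04 | 3% |
| 0.30 vs 0.30 | 3/39 = 0.0769 | 0 | 0.00 | nominal |

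**Check on the first rejection rate.** Records per person: 36 + 0.1·10·0.60 + 0.9·10·0.30 = 39.3. Exposed share: 4.2/39.3 = 0.107. Flare-window share: 3.3/39.3 = 0.084. Residual variance: 1.5² + 0.084·0.916·2.5² = 2.73. Standard error: √[2.73/(440·38.3·0.107·0.893)] = 0.041. So z = 0.165/0.041 = 4.0, and the chance of passing the two-sided 0.005 threshold (2.81) is about 88%, against 87% simulated.

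**Scheduled records only.** The F·q terms drop out and the expected slope is zero. The simulations agree.

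**Flare OR and NRS slope together.** A second null simulation drew pain day by day and let participants start flare-window records on high-pain days, so both estimates came from the same data. Its assumptions are between-person SD 1.8, within-person SD 1.5, and a starting probability of 15% on unexposed high-pain days. It used 200 replications, a person-stratified Mantel-Haenszel OR and a person-demeaned slope.

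| Mechanism (no true effect) | OR, all | NRS slope, all | OR, scheduled | NRS slope, scheduled |
|---|---|---|---|---|
| No bias | 1.01 | 0.00 | 1.01 | 0.00 |
| Selective starting, ratio 1.5 | 1.37 | +0.15 | 0.99 | 0.00 |
| Selective starting, ratio 2 | 1.73 | +0.27 | 1.01 | 0.00 |
| Selective starting, ratio 3 | 2.47 | +0.49 | 1.00 | 0.00 |
| Labelling only (scheduled records), ratio 2 | 1.38 | 0.00 | 2.19 | 0.00 |
| Flares logged at ordinary pain on 5% of exposed days | 2.30 | −0.20 | 1.00 | 0.00 |
| Activity over-reported on 5% of high-pain records | 1.47 | +0.25 | 1.48 | +0.17 |

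Under selective starting, both all-records estimates rise together and both scheduled-only estimates stay at the null. Labelling bias and flares logged at ordinary pain are exposed by the all-records NRS model. Pain-dependent recall of activity escapes both record sets. With a starting ratio of 2, the all-records slope was +0.28 at activity frequencies of 5% and 25%. With few flare-window records (about 7% of the total) it fell to +0.14.

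**The case against.** Several stronger readings are tempting, and the documents do not support them.

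- **That the plan states the NRS model reuses flare-window records.** It does not. This is inferred from the word analogous, and the Figure 3 footnote belongs to the binary flare analysis. What can be said is that the record set is unspecified and pooling is the natural reading.
- **That the NRS model carries the whole bias and is no check.** It removes pure labelling bias (slope 0.00 with the OR at 1.38) and exposes flares logged at ordinary pain (slope −0.20 with the OR at 2.30).
- **That the plan treats similar directions as proof of no bias.** It says only that no bias implies similar directions. The converse is a reader's step, though an easy one to take.
- **That flare-window NRS is high by construction.** No NRS threshold defines a flare. Section 3.0 describes it through pain and functional impact, so higher NRS is an assumption here.
- **That pooling by itself creates bias.** With equal logging the slope is zero.

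The plan also has other safeguards: an open-ended list of possible biases in 5.6.2a, sensitivity analyses promised in 5.1, declining payment, staff contact, and withdrawal for inappropriate flare entries (5.7). These are general statements or conduct measures, and none specifies an analysis of selective logging. The calculations leave out the adjustment for prior NRS, prior flares and time-varying confounders that an analogous model would carry. Since the selection acts on whether the current record is created, there is no evident reason for that adjustment to remove it, but this was not tested.

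Nor are scheduled-only data a clean reference. Besides pain-dependent recall, activity avoidance during ongoing flares biases them: a null simulation with 3-day flares and activity cut to 40% during flares gave −0.08. Finally, NRS is a secondary outcome, and section 5.6.2 calls the analysis plans preliminary.

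**Conclusion.** The concern holds in a limited form. The claim that the NRS model accounts for self-identification bias is too broad: it covers labelling, but not selective starting of flare-window records if those records are pooled. Under that bias, agreement between the flare OR and the NRS slope is uninformative.

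The size depends on logging behaviour that the documents do not describe: from zero with equal logging, through about +0.04 and +0.09, to +0.16 NRS points when exposed participants log twice as often. In the second simulation, a starting ratio of 2 gave a spurious OR of 1.73, inside the 1.5–2.0 range that section 5.6.1 regards as meaningful. The direction rests on two conditions: flare-window NRS exceeds scheduled NRS, and exposed participants start more records. Neither is established by the documents, and no specified analysis would show whether selective logging had occurred. The change is worth making, but the point does not invalidate the primary model.

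**What to change.** In section 5.6.2a:

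1. State which e-Questionnaires enter the NRS mixed model.
2. Add, as the check on self-identification bias, the NRS model and the flare model fitted on scheduled e-Questionnaires only, reported beside the all-records results. Use a within-person activity term in the NRS model (for example, activity centred on the person's mean) so that it targets the same effect as equation 1. Both models are needed, because the scheduled-only flare model can still carry labelling bias.
3. Narrow the claim: the all-records NRS model addresses labelling of flare status, not selective initiation of flare-window records. Say also that agreement in direction does not by itself exclude bias.

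The cost is a few lines of text and one re-run on a subset of data already being collected. The check gives up the flare-window records and so loses precision. Up to 36 scheduled records per person remain, and the power estimates for the flare outcome already assume scheduled records only; the plan gives no such estimate for the NRS slope. The text should acknowledge that the scheduled-only check does not remove pain-dependent recall of activity or activity avoidance during ongoing flares. The primary all-records flare model is unchanged.
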